# 1. Study Synopsis

Title Of Clinical Trial:	A randomised controlled trial of the clinical and cost-effectiveness of extended-release naltrexone and oral naltrexone
Protocol Short Title/ Acronym:	Naltrexone Enhanced Addiction Treatment trial (NEAT)
Study Phase If Not Mentioned In Title:	Phase III clinical trial of an investigational medicinal product
Purpose Of Clinical Trial:	The NEAT trial is for adults with a diagnosis of opioid use disorder (DSM5) in the past year, who are now detoxified (zero opioid tolerance) and want help to stay away from heroin. The primary purpose of the trial is to evaluate the clinical and cost-effectiveness of enhanced naltrexone (NTX) relapse prevention therapy programme for the treatment of opioid use disorder (following NICE, 2007). The NEAT trial will evaluate two formulations of this medication: a 90-day implanted, long-acting form (XR-NTX; 'iGen/Atral-Cipan' device herein), and a short-acting oral tablet form (O-NTX, the active comparator).
	A. Is XR-NTX treatment more effective than placebo at reducing heroin use?
	B. Is XR-NTX more effective than O-NTX at reducing heroin use?
Primary Objective:	C. Is XR-NTX more cost- effective than placebo in terms of quality-adjusted life years?
	D. Is XR-NTX more cost-effective than O-NTX in terms of quality-adjusted life year?
	A. To compare treatment retention and medication and psychological intervention adherence rates among the XR-NTX, O-NTX and placebo conditions.
	B. To contrast the XR-NTX, O-NTX and placebo conditions on quality of life indices.
	C. To contrast XR-NTX, O-NTX and placebo conditions on:
	heroin and cocaine craving;
	
 
self-reported opioid, cocaine, amphetamine and benzodiazepine use (with past 48 hour abstinence verified via urine drug screening [UDS]);
 

Secondary Objectives:	alcohol use;
	injection health risk behaviours;
	
 
psychological health (depression and anxiety symptoms);
 

	molecular (genetic) biomarkers of treatment response.
	
 
Plasma naltrexone and 6-β-naltrexol (the primary metabolite of NTX);
 

	D. To document the safety of XR-NTX and O-NTX.
	E. To compare patterns of heroin relapse among the XR-NTX, O-NTX and placebo conditions
Trial Design:	A three-year definitive, three-centre, three-arm, parallel group, placebo controlled, double-blind, double-dummy, randomised clinical trial, with primary outcomes assessed 12 weeks after randomisation, and with clinic

	conducted research follow-ups staged at 16, 24 and 36 weeks.
Clinical settings:	Two specialist NHS outpatient addiction clinics in London and Birmingham.
Primary Endpoints:	Clinical: the proportion of heroin negative UDS results at the end of the 12 week post-randomisation period (denominator 36), with contrasts for: (i)XR-NTX vs. placebo, and (ii) XR-NTX vs. O-NTX.
	Economic: health related quality of life and cost-effectiveness at 36 weeks with comparisons for (i) XR-NTX vs. placebo, and (ii) XR-NTX vs, O-NTX.
Sample Size:	300 adult patients
	1 iGen/Atral-Cipan XR-NTX device (765mg naltrexone or Placebo) at Day 0 of Study Week 1.
Imp, Dosage And Route Of Administration:	3 x weekly directly observed (clinic supervised) active or placebo O-NTX tablets (2 x 50mg, Monday and Wednesday; 3 x 50mg, Friday) at Day 0 of Study Week 1 (for 4 weeks) and then an 8 week regimen of patient administered dosing at the same dosing level contingent on return of medication packaging and reports of dosing.
	(NB: The higher dose given on Fridays provides extended therapeutic coverage for the patient because the clinic is closed at the weekend).
	Project start: September 2014
Estimated time line	First patient in: March 2015
Latinated time line	Last patient out: December 2017
	Project end: May 2018
Protocol status (draft/ final)	Final
Version And Date Of Final Protocol:	3.0 (27.07.15)
Version And Date Of Protocol	2.0 (26.09.14)
Amendments:	1.11 (13.08.14)

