#### 6.5.2 Follow up

There are three follow-up assessments: at 16, 24 and 36 weeks Each of these follow-ups is trial nurse-administered and held in a private clinical room at the recruitment centre. A long recognised problem in conducting outcome studies with drug users is the difficulty in following up participants for research interviews, particularly where patients have dropped out of treatment and are no longer in contact with the treatment service. To overcome this potential problem, information will be collected from patients at the beginning of the study that will assist researchers in tracking patients. This will include postal addresses and telephone numbers of patients, contact details of at least one locator individual (e.g. a family member, friend or recovery mentor), and permission to contact authorities such as general practitioners. Patients will be given assurances that all attempts to contact them will be confidential, and the purpose of the researchers seeking contact will not be disclosed to others. Patients will be reimbursed for their travel costs to attend clinic visits, and will also receive a high street store voucher worth £20 in return for the time taken to attend each of the three 60 minutes post-treatment follow-ups

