## 7. Selection and Withdrawal of Participants

## 7.1 Inclusion Criteria

Inclusion criteria for the study are intended to be as close to clinical practice as possible. Each participant in the trial must meet all of the following criteria:

- 1. Is 18 years of age or older.
- 2. Can demonstrate a verbal understanding of the study patient information material, is able to provide written consent, and can understand and confirm willingness to comply with the protocol.
- 3. Has a diagnosis of opioid use disorder based on the criteria of the Diagnostic and Statistical Manual of Mental Disorders, Fifth Edition (DSM5: past 12 months),) conducted at baseline.
- 4. Is completing or has recently completed an inpatient or outpatient treatment for opioid detoxification, or has been completely and continuously abstinent from all opioids for at least seven days.
- 5. Has no tolerance to opioids, as verified by a negative urine toxicology screening test prior to randomisation (using an instant result immunoassay device).
- 6. Passes a naloxone challenge test (to confirm zero opioid tolerance by demonstrating no clinical sign or subjective report of opioid withdrawal before randomisation and prior to implant procedure) NB: Individuals failing screening will be allowed to enter screening as clinically indicated.
- 7. Is voluntarily seeking opioid antagonist treatment for opioid use disorder.
- 8. Lives in stable/secure accommodation in the community.

9. Has a personal (mobile/cellular) phone, and is able to nominate at least one locator individual (e.g. a family member, friend or recovery mentor) with a verifiable address and a telephone number to assist with the arrangement of follow-up appointments as required.

10. If female, is not pregnant or breast feeding and agrees to use a birth control method (either oral hormonal contraceptives, barrier [condom or diaphragm], or Nexplanon implant) for the duration of the study.

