#### 12.1 Power calculation

Estimated treatment effect size and retention to guide the required number of participants for NEAT was based on best available trial evidence and meta-analysis. The trial is designed to compare the effectiveness of extended-release naltrexone (XR-NTX) and oral tablet naltrexone (O-NTX) on an intention-to-treat basis at 12 weeks post-randomisation. There are two comparisons: XR-NTX vs. placebo, and XR-NTX vs. O-NTX. Based on a 2007 HTA systematic review and the naltrexone depot trial by [name] and her colleagues in the USA, the following assumptions were made:

- A. The mean percentage of heroin-free urine drug screens at 12 weeks post-randomisation will be approximately 0.30 (30%) in the placebo and O-NTX treatment arms, respectively, and 0.55 (55%) in the XR-NTX treatment 
- B. The standard deviations of the treatment groups will be of a similar magnitude We estimate the common standard deviation to be 30.
- C. The minimal clinically significant difference between the XR-NTX and O-NTX / placebo group will be a 25 point difference in percentage observable at 12 weeks post-randomisation, equating to an effect size of 0.8.
- D. An expected 40% attrition rate based on previous trial data.
- E. To control for multiple comparisons in the primary analyses, Bonferroni correction has been applied to the significance level reducing it by a factor 2. Thus the significance level will be considered at 2.5%.

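### The week 16, 24 and 36 follow-ups are set as clinic visits with no fallback mode, so participants who will not return have no observed week-36 EQ-5D or AD-SUS

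*Protocol*

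**What the plan says.** The Protocol synopsis (section 1, Trial Design) sets out clinic "conducted research follow-ups staged at 16, 24 and 36 weeks". Section 6.5.2 is more explicit: "Each of these follow-ups is trial nurse-administered and held in a private clinical room at the recruitment centre". No section describes collection by telephone, post, internet or home visit.

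Section 6.5.2 acknowledges that follow-up is difficult in this population, "particularly where patients have dropped out of treatment and are no longer in contact with the treatment service". It responds with two measures:

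- Tracing: "This will include postal addresses and telephone numbers of patients, contact details of at least one locator individual".
- Payment for coming in: "Patients will be reimbursed for their travel costs to attend clinic visits, and will also receive a high street store voucher worth £20", for the time taken to attend each follow-up.

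Inclusion criterion 9 (section 7.1) adds: "Has a personal (mobile/cellular) phone, and is able to nominate at least one locator individual". The stated purpose of the locator details is "to assist with the arrangement of follow-up appointments as required".

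The schedule (6.3) and instrument list (8.10) place EQ-5D and AD-SUS at screening, week 12 and week 36 only. Section 7.5 asks for the TOP and the withdrawal form at withdrawal, and 6.3 and 8.10 add self-report substance-use forms. Neither EQ-5D nor AD-SUS is on any of those lists. Section 11 makes QALYs from EQ-5D the primary economic outcome measure and takes external resource use and crime from participant interview at baseline, after the 12-week treatment period and at week 36. Section 11.2 would fill missing EQ-5D by last value carried forward and missing total cost by single regression imputation, on the expectation of about 5% missing.

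**The concern.** The protocol names the group it expects to lose, namely people who have left treatment and broken contact with the service. The only mode it then fixes requires them to return to that service. Tracing, travel costs and the voucher help those willing to come back and do little for those who are not.

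At week 36 only the urine test and the optional biomarker swab need the participant in the room. EQ-5D and AD-SUS need no specimen or examination.

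Primary objectives C and D are at stake. If non-return is related to relapse, the observed week-36 values are selected towards participants who are doing better. If relapse differs by arm, so does the selection. For EQ-5D the planned substitute is the last earlier value. After week 12 all study medication stops (6.4.3), so an end-of-treatment utility would stand in for the post-treatment period in the very people who did not return. A later analysis can change the imputation method but cannot restore data that were never collected.

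**Working it through.** **1. The plan's own figure.** Section 12.2 states 98% power. With 100 × (1 − 0.40) = 60 per arm, effect size 0.8 and two-sided alpha 0.025, the normal approximation gives 98.4% (98.2% by noncentral t). With 25/30 as the effect size it gives 99.0%. The stated figure is reproduced. It concerns the 12-week urine outcome, and "An expected 40% attrition rate based on previous trial data" is an input to that calculation.

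**2. How many could lack week-36 data.** The documents give two rates, neither stated specifically for the week-36 visit:

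| Source | Rate | Missing of 300 | Observed per arm | Complete-case SE against full data |
|---|---|---|---|---|
| 11.2, economic data | 5% | 15 | 95 | √(1/0.95) = 1.03 |
| 12.1, 12-week comparison | 40% | 120 | 60 | √(1/0.60) = 1.29 |

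Applying 40% at week 36 is an assumption. The two rates differ by a factor of 120/15 = 8.

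**3. Precision regained by telephone.** Assume telephone reaches 25% or 50% of the missing (not in the documents).

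- At 40% missing: 60 per arm becomes 70 or 80. √(60/70) = 0.926 and √(60/80) = 0.866, so the SE falls by 7% or 13%.
- At 5% missing: 95 per arm becomes 96.25 or 97.5. √(95/96.25) = 0.993 and √(95/97.5) = 0.987, so the SE falls by 0.7% or 1.3%.

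**4. Illustrative bias.** Assume 30% missing in one arm and 50% in the other, with non-attenders 0.10 lower in utility (none of these values is in the documents). The complete-case mean in an arm is too high by 0.10 × its missing share. The error in the arm difference is 0.10 × (0.50 − 0.30) = 0.020 utility, in favour of the arm with more missing.

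**5. Conversion to QALYs.** Assume a linear area under the curve through weeks 0, 12 and 36. Week 36 then carries (36 − 12)/2 = 12 weeks of weight. Week 12 carries 12/2 + 24/2 = 18 weeks.

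- Only week 36 missing: 0.020 × 12/52 = 0.0046, about 0.005 QALY.
- Week 12 missing too: 0.020 × (12 + 18)/52 = 0.0115, about 0.012 QALY.

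**6. If half of the missing were recovered at random.** The arm means fall by 0.10 × 0.15/0.85 = 0.0176 and 0.10 × 0.25/0.75 = 0.0333. The correction to the difference is 0.0157, leaving 0.020 − 0.0157 = about 0.004 utility. This is a best case, since those who answer the phone are unlikely to be a random half.

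**The case against.** **Remote contact is not forbidden.** A reader might infer that 6.5.2 rules out any other mode. It does not. It names a setting, section 7.5 promises efforts to obtain follow-up data from those who stop study drug only without naming a mode, and section 11 gives no location for the resource-use interview. This stands: the gap is an unstated fallback, and adding one would contradict nothing.

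**Non-returners are imputed, not excluded.** Section 11.2 plans imputation, says the low-missingness assumption will be checked, and allows other methods. This also stands. What is lost is the observed value, and the complete-case error above does not model the planned analysis.

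**The size may be small.** The protocol's own expectation for economic data is about 5%, at which the precision gain is around 1%. A reader might take the 40% as the expected loss at week 36, but the document states it for the 12-week comparison. A reader might also spread 0.020 utility over the whole 36 weeks (0.020 × 36/52 = 0.014 QALY). That would put the error at baseline too, where EQ-5D is collected at screening.

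**Clinic attendance has reasons.** Urine is tested at each follow-up, self-reported abstinence is to be verified by it (6.2.2), and a private room suits an interview that covers crimes committed. Owning a phone at entry does not guarantee being reachable at week 36. These points support keeping the clinic visit as first choice. They do not argue for having no data when it fails.

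**The trial is closed.** Section 25 records a decision in November 2016 to wind down, with six participants recruited. The practical value now lies mainly in the future implant trial that section 25.1 aims to inform.

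**Conclusion.** The point holds as a cheap, worthwhile improvement to data collection. The follow-ups are fixed as visits to the recruitment centre with no stated fallback, and the two instruments behind the primary economic endpoint have no other collection point after week 12. A participant who will not attend therefore has no observed week-36 EQ-5D or AD-SUS.

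The size is not settled by the documents. Between 15 and 120 of 300 could be affected. The gain in standard error ranges from about 1% to 7–13%, depending on which missingness rate applies and on an assumed telephone reach of 25–50%. The bias figures of about 0.005 to 0.012 QALY are illustrative. They rest on assumed missingness of 30% and 50%, an assumed 0.10 utility gap, linear interpolation and a complete-case analysis, and how much telephone contact would remove depends on who can be reached.

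A reader might extend the point to the trial's main result. The documents do not support that: the primary clinical endpoint uses the 36 urine tests of weeks 1–12 and is untouched by how the later follow-ups are held.

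**What to change.** In section 6.5.2 and the synopsis, keep the clinic visit as first choice and add a fallback:

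- If a participant cannot or will not attend within the visit window, the blinded trial nurse completes at least EQ-5D and AD-SUS by telephone and, where feasible, PHQ-9, GAD-7, the 28-day substance use form and the heroin use form, as scheduled for that visit.
- Urine (and the optional swab at week 36) is recorded as missing, and the mode of completion is recorded on the eCRF.
- The £20 voucher is worded to cover a completed telephone follow-up.
- The same rule applies to the week-12 EQ-5D and AD-SUS for participants who have stopped attending.

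The cost is a few sentences of protocol text, one eCRF field and some staff time for call attempts. The downsides are that self-report by telephone is not verified by urine, privacy is less assured than in a clinic room, and there may be a small mode effect, which the recorded mode allows the analysis to examine.

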# 2. Glossary of terms

Abbreviation	Definition
AE	Adverse Event
AR	Adverse Reaction
CRF	Case Report Form
DMC	Data Monitoring Committee
GCP	Good Clinical Practice
IMP	Investigational Medicinal Product
ISRCTN	International Standardised Randomised Controlled Trial Number
MHRA	Medicines & Healthcare products Regulatory Agency
КСТИ	King's Clinical Trials Unit, King's College London
КНР-СТО	King's Health Partners Clinical Trials Office
NICE	National Institute for Health and Care Excellence
NIHR	National Institute for Health Research
NTX	Naltrexone
O-NTX	Naltrexone (oral tablet)
XR-NTX	Naltrexone (extended release implant)
OST	Opioid Substitution Therapy
REC	Research Ethics Committee
SAE	Serious Adverse Event
SOP	Standard Operating Procedure
SPC / SmPC	Summary of Product Characteristics
SUSAR	Suspected Unexpected Serious Adverse Reaction
TMG	Trial Management Group
TSC	Trial Steering Committee
UDS	Urine Drug Screen

#### Inclusion criteria Exclusion criteria 18 years + Clinically significant medical condition or observed abnormalities on physical examination or laboratory investigation Can demonstrates a verbal understanding of the PIL, is able to provide written consent and can confirm willingness to Severe alcohol dependence and/or alcohol withdrawal Opioid withdrawal syndrome, current comply with the protocol Has a diagnosis of opioid use disorder (past 12 months) Clinical diagnosis of opioid dependence syndrome according based on the criteria of the DSM5 Positive naloxone challenge test prior to randomisation Is completing or has recently completed an inpatient or Positive test for presence of opioids in urine outpatient treatment for opioid detoxification, plus abstinent Hepatic insufficiency or Active hepatitis Use of O-NTX or XR-NTX within 90 of screening continuously from opioids for at least 7 days · Has no tolerance to opioids, as verified by a negative urine Consent Current criminal justice involvement with legal proceedings toxicology screening test prior to randomisation Current (past 30 day) suicidal planning or recent (past six months) · Passes a naloxone challenge test to confirm zero opioid suicide attempt Active, uncontrolled severe mental illness and/or a history or tolerance and no clinical or subjective report of opioid Screening withdrawal evidence of organic brain disease or dementia Voluntarily seeking opioid antagonist treatment Severe renal impairment evaluated by clinical decision assessments, Urine Lives in stable/secure accommodation in the community Icenko-Cushing syndrome Drug Screen, Has a personal mobile phone and nominates a locator Systemic mycoses Naloxone challenge Clinical history of glaucoma individual, with a verifiable address and phone number to assist with arrangements of follow up appointments Clinical history of osteoporosis Not pregnant and willing to use birth control Currently breast-feeding History of hypersensitivity to opioid receptor blockers Randomisation 1:1:1 History of hypersensitivity to triamcinolone or related compounds (Stratified by centre, referral Current participation in any interventional trial, or completed and illicit cocaine use) participation in any interventional trial within the last 3 months Begin intervention Active XR-NTX Placebo XR-NTX Placebo XR-NTX Placebo O-NTX Active O-NTX Placebo O-NTX (3 times weekly) (3 times weekly) (3 times weekly) 1 x weekly clinical case management sessions (Weeks 1-12) MoCA (Screening and week 12) 3 x weekly UDS (Weeks 1-12, 16, 24 and 36) ECG, OST treatment history, Personality disorder screener, Substance in last 7 days (Weeks 1-12 and withdrawal) BPAQ-SF, BIS-11, breathalysed alcohol test, naloxone MCCS Heroine and cocaine (adapted) (Weeks 1-12, 16, 24 and 36) challenge (Screening) Withdrawal . Optional 6x plasma monitoring assessments (Weeks 1-4, 8 and 12) Physical examination (Screening, weeks 1-4, 8 and 12) TOP SCID-I CV and optional biomarker screening (Screening and week 36) Haematology, biochemistry (Screening, weeks 4, 8 and 12) withdrawal Substance diagnostic form, ADAPT, HRBS, PHQ-9, GAD-7, WSAS, Substance use in last 28 days (Screening and weeks 16, 24 Withdrawal ADSUS, EQ5D (Screening, weeks 12 and 36) form Top scales (Screening, weeks 12, 36 and withdrawal) Heroin use during follow up (Weeks 24 and 36) Substance Ongoing-Conmeds and AE reporting abuse form End points and analysis Primary Clinical: the proportion of heroin negative UDS results at the end of the 12 week post-randomisation period (denominator 36), with contrasts

for: (i) XR-NTX vs. placebo, and (ii) XR-NTX vs. O-NTX.

Economic: health related quality of life estimated using the EQ5D5L and cost-effectiveness at 36 weeks.

Treatment retention, adherence, heroin and cocaine craving scores, self-reported opicid, cocaine, amphetamine, benzodiazepine (and their active class metabolites via urine drug screening), and alcohol use, injection health risk behaviours, psychological health (depression and anxiety symptoms), and health-related quality of life results over the 12 weeks from randomisation and at 1, 3 and 6 months follow-up.

		26
	INFORMED CONSENT	_
8.3	VITAL SIGNS	27
8.4	PLASMA MONITORING	27
8.5	BIOLOGICAL TESTING OF OPIOID, COCAINE, AMPHETAMINE AND BENZODIAZEPINE USE	28
8.6	NALOXONE CHALLENGE	28
8.7	BREATHALYSED ALCOHOL LEVEL	28
8.8	SELF-REPORTED SUBSTANCE USE	28
8.9	MOLECULAR BIOMARKER SCREENING (GENOTYPING)	28

8.10	STRUCTURED CLINICAL INTERVIEWS AND INSTRUMENTS	29
8.11	LABORATORY TESTS	29
9. AS	SSESSMENT OF EFFECTIVENESS	29
9.1	PRIMARY EFFECTIVENESS PARAMETERS	30
9.2	SECONDARY EFFECTIVENESS PARAMETERS	30
10.	ASSESSMENT OF SAFETY	30
10.1	SPECIFICATION, TIMING AND RECORDING OF SAFETY PARAMETERS.	30
10.2	PROCEDURES FOR RECORDING AND REPORTING ADVERSE EVENTS	31
10.3		
10.4	TREATMENT STOPPING RULES	33
11.	ECONOMIC EVALUATION	33
11.1	Costs	33
11.2	COST-EFFECTIVENESS ANALYSIS	33
12.	STATISTICS	34
12.1	Power calculation	34
12.2	ESTIMATED REQUIRED SAMPLE SIZE	35
12.3	RANDOMISATION	35
12.4	Analysis	35
13.	TRIAL STEERING COMMITTEE	35
14.	DATA MONITORING COMMITTEE	36
15.	TRIAL MANAGEMENT GROUP (TMG)	36
16.	DIRECT ACCESS TO SOURCE DATA AND DOCUMENTS	37
17.	ETHICS & REGULATORY APPROVALS	37
18.	QUALITY ASSURANCE	37
18.1		
19.	DATA HANDLING	
19.1		
	DATA MANAGEMENT	
20.1		
21.	PUBLICATION POLICY	
22.	INSURANCE / INDEMNITY	
23.	FINANCIAL ASPECTS	39
24.	TIME TABLE	39
25.	LEARNING LESSONS FROM THE CLOSURE OF THE NEAT TRIAL: QUALITA	ATIVE FOLLOW-UP
	41	
25.1		
25.2		
25.3 25.4		
25.4 25.5		
25.6		
25.7		
25.8		

Study	Protocol: Version: 6.0 20.06.2017	EudraCT Number: 2013-002584-25
26.	SIGNATURES	47

